5.2.2.17 After Every 2 Cycles

- 1) Assess for AEs and SAEs
- 2) Update concomitant medications

- 3) Perform CXR, CT or MRI scan (disease assessments must be performed within 7 days prior to the planned start of the next cycle)

5.2.2.18 End of Treatment Visit

This visit is to be conducted at the time a decision is made for a subject to discontinue MEDI-565 treatment due to PD, initiation of alternative anticancer therapy, unacceptable toxicity, or other reasons.

- 1) Perform physical examination
- 2) Record weight
- 3) Record vital signs and pulse oximetry
- 4) Record ECG
- 5) Assess Karnofsky Performance Status
- 6) Perform Mini Mental State Exam and gait assessment
- 7) Assess for AEs and SAEs
- 8) Update concomitant medications
- 9) Collect blood samples for end of treatment (EOT):
 - Serum chemistry (including soluble CEA)
 - Hematology
 - Coagulation parameters
 - Concentrations of MEDI-565
 - Anti-MEDI-565 antibodies
 - Circulating tumor cells
 - Flow cytometric analysis
 - Circulating cytokines
 - Circulating soluble protein biomarkers
- 10) Collect urinalysis sample
- 11) Perform CXR, CT or MRI scan (unless it has been performed within 14 days of treatment discontinuation)

Note: If the End of Treatment visit occurs on the same day as another treatment visit or a post treatment visit, only perform one of the same evaluations and avoid duplication of evaluations.

5.2.3 Post-Treatment Follow-up Period

5.2.3.1 30 Days (plus or minus 3 Days) Post-treatment

This visit is only required for subjects who discontinue treatment for a reason other than disease progression.

- 1) Perform physical examination
- 2) Record weight
- 3) Record vital signs and pulse oximetry
- 4) Record ECG
- 5) Assess Karnofsky Performance Status
- 6) Perform Mini Mental State Exam and gait assessment
- 7) Assess for AEs and SAEs
- 8) Update concomitant medications
- 9) Collect blood samples for post-treatment follow-up:
 - Serum chemistry (including soluble CEA)
 - Hematology
 - Coagulation parameters
 - Concentrations of MEDI-565
 - Anti-MEDI-565 antibodies
 - Circulating tumor cells
 - Flow cytometric analysis
 - Circulating cytokines
 - Circulating soluble protein biomarkers
- 10) Collect urinalysis sample
- 11) Perform CXR, CT or MRI scan (only required for subjects who discontinued treatment without progressive disease and who have not initiated alternative anticancer therapy)

5.2.3.2 3 Months Post End of Treatment

- 1) Perform physical examination (only for subjects who discontinued treatment without progressive disease and who have not initiated an alternative anticancer therapy)
- 2) Record subsequent anticancer therapy

- 3) Record survival status
- 4) Collect blood samples for post-treatment follow-up
 - Complete blood count (CBC) (performed only at 3 months post-treatment)
 - Flow cytometric analysis (performed only at 3 months post-treatment)
- 5) Perform CXR, CT, or MRI scan (only for subjects who discontinued treatment without progressive disease and who have not initiated an alternative anticancer therapy)

5.2.3.3 6 Months and Every 3 Months (plus or minus 7 Days) Post-treatment

This visit may be conducted by telephone if CXR, CT, or MRI scan is not completed. Visits every 3 months post-treatment should be continued until disease progression is documented.

- 1) Record subsequent anticancer therapy
- 2) Record survival status
- 3) Perform CXR, CT, or MRI scan (only for subjects who discontinued treatment without progressive disease and who have not initiated an alternative anticancer therapy)

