Withdrawal of consent: If consent is withdrawn, the subject will not receive any further investigational product or further study observation. Note that the subject may need to undergo additional tests or tapering of treatment to withdraw safely.

Lost to follow-up: Subjects will be considered lost to follow-up only if no contact has been established by the time the study is completed such that there is insufficient information to determine the subject's status through end of study (defined as 1 year after the final subject is entered into the study or the date the study is closed by the sponsor).

- Note: Subjects refusing to return to the site or to continue participation in the study should be documented as “withdrawal of consent” rather than “lost to follow-up.” Investigators should document attempts to re-establish contact with missing subjects throughout the study period. If contact with a missing subject is re-established, the subject should not be considered lost to follow-up and any evaluations should resume according to the protocol.

Permanent discontinuation of investigational product: Subjects who are permanently discontinued from further receipt of investigational product, regardless of the reason (withdrawal of consent, due to an AE, other), will be identified as having permanently discontinued treatment. Subjects who permanently discontinue treatment may either be considered to have completed the study or not to have completed the study (see Section 4.6).

Subjects who are permanently discontinued from receiving investigational product will be followed for safety through the full study period through 30 days after the last administration

of MEDI-565, including the collection of any protocol-specified blood or urine specimens, unless consent is withdrawn, lost to follow-up, or enrolled in another clinical study. In addition, subjects will be followed for disease evaluations every 3 months (\pm 2 weeks) until disease progression, death, initiation of alternative anticancer treatment, withdrawal of consent, or end of study (defined as 1 year after the last subject begins treatment or the date the study is closed by the sponsor), and for survival every 3 months until death, withdrawal of consent, or end of study.

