6.4 Reporting Requirements for Safety Parameters

6.4.1 Study Reporting Period and Follow-up for Adverse Events

The reporting period for AEs is the period immediately following the time that written informed consent is obtained through 30 days after the last dose of MEDI-565. New (nonserious) AEs that start after the reporting period will not be collected.

All AEs will be followed to resolution through the end of subject participation in the study, even if the date extends beyond the reporting period.

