6.4.2 Reporting of Serious Adverse Events

6.4.2.1 Study Reporting Period and Follow-up for Serious Adverse Events

The reporting period for SAEs is the period immediately following the time that written informed consent is obtained through 30 days post the subject’s last dose of treatment or until the subject begins another anticancer therapy. After submitting an initial SAE report for a subject (to MedImmune Patient Safety), the investigator is required to follow the subject proactively and provide further information on the subject’s condition to MedImmune Patient Safety.

At any time after completion of the study, if an investigator or qualified designee becomes aware of an SAE that is suspected by the investigator or qualified designee to be related to investigational product, the event must be reported to MedImmune Patient Safety.

The investigator is responsible for following all SAEs until resolution, until the subject returns to baseline status, or until the condition has stabilized with the expectation that it will remain chronic, even if this extends beyond study participation.

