7.2 Analysis Populations

The Evaluable Population for DLT includes all subjects enrolled in the dose-escalation phase who received at least one full cycle of MEDI-565 and completed safety follow-up through the DLT evaluation period (defined in Section 4.5.4.5) or experience any DLT. The Evaluable Population for DLT will be used for the MTD evaluation.

The Safety Population includes all subjects who receive any investigational product.

The Per-Protocol Population will include all subjects who complete 2 cycles of treatment or discontinue treatment due to disease progression or toxicity.

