7.3 Endpoints

7.3.1 Primary Endpoints

The primary endpoints are as follows:

- The number (percentage) of subjects with a DLT will be summarized by dose level and overall. The MTD evaluation will be based on the evaluable population for DLT.
- The OBD will be determined based upon analysis of all available subject data including safety, PK, pharmacodynamic, biomarker, and antitumor activity data.
- The number (percentage) of subjects with AEs and SAEs reported through 30 days after the last dose of MEDI-565 will be summarized for all subjects who received at least one dose of study drug (Safety Population). Adverse events and SAEs will be graded according to the [NCI CTCAE v4.03](#) and described by system organ class using the Medical Dictionary for Regulatory Activities (MedDRA) preferred term, severity, and relationship to MEDI-565. Frequency rates will be calculated for each system organ class and MedDRA preferred term.
- The number (percentage) of subjects with significant or important clinical findings in ECG will be summarized by dose cohort.
- The number (percentage) of subjects who had clinically significant laboratory changes recorded as AEs will be summarized. Laboratory hematology and chemistry values will be summarized with the worst value during the study by dose cohort. Clinically significant coagulation profile and urinalysis results will be described.

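### The 30-day post-treatment visit is waived after progressive disease, although the safety follow-up rules and the primary safety endpoint run to 30 days after last dose with no such exception

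*Protocol*

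**What the plan says.** Protocol 5.2.3.1 lists the 30-day procedures: physical examination, weight, vital signs and pulse oximetry, ECG, performance status, mental state and gait, AE/SAE assessment, concomitant medications, blood samples, urinalysis and a scan. It opens by limiting who attends: "This visit is only required for subjects who discontinue treatment for a reason other than disease progression".

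Other sections set 30-day safety follow-up without that limit:

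- **4.2.3**, on permanent discontinuation for any reason: subjects are "followed for safety through the full study period through 30 days after the last administration", with protocol-specified specimens. Its exceptions are withdrawn consent, loss to follow-up and enrolment in another study. PD is not among them.
- **6.4.1**: AEs are reportable from when "written informed consent is obtained through 30 days after the last dose of MEDI-565".
- **7.3.1**, a primary endpoint: "The number (percentage) of subjects with AEs and SAEs reported through 30 days after the last dose of MEDI-565 will be summarized". The population is defined in 7.2: "The Safety Population includes all subjects who receive any investigational product".
- **5.3.1**: weight and vital signs are due at 30 days post-treatment, and an ECG is due then for all subjects.
- **Table 5.2-2**: the day-30 column has no footnote restricting it by reason for stopping.

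For SAEs, 6.4.2.1 sets the period to 30 days after last dose "or until the subject begins another anticancer therapy". Neither 6.4.1 nor 7.3.1 contains that alternative end.

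**The concern.** A site cannot follow both the waiver in 5.2.3.1 and the unrestricted requirements in 4.2.3 and 5.3.1. If sites follow the waiver, subjects who stop for PD have no scheduled AE/SAE assessment at the end of the window over which the primary safety endpoint is counted, while subjects who stop for any other reason do. Evaluating the safety profile is part of the primary objective of this first-in-human study. The percentage of subjects with an AE or SAE to day 30 would then rest on scheduled ascertainment for some subjects and on spontaneous reporting for others, with reason for stopping deciding which.

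**Working it through.** There is no stated sample size, power or error rate to reproduce here. The check is a comparison of sections followed by day counting.

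**1. Which visits can carry an AE assessment after last dose in a subject who stops for PD?**

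| Contact | Source | AE/SAE assessment? | Applies after PD? |
|---|---|---|---|
| Days 8, 15, 22 of the cycle | 5.2.2.6-8, 5.2.2.14-16 | Yes | Yes, while the cycle's visits continue |
| After every 2 cycles | 5.2.2.17 | Yes | Yes, at the scan that finds PD |
| End of Treatment | 5.2.2.18 | Yes | Yes; PD is named, and timing follows the decision to stop |
| 30 days post-treatment | 5.2.3.1 | Yes | Waived |
| 3 months, 6 months and 3-monthly | 5.2.3.2, 5.2.3.3, Table 5.2-2 | No | AE assessment not listed |

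The End of Treatment visit is therefore the last scheduled AE/SAE assessment after PD, and it is not tied to 30 days after last dose.

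The scan item within 5.2.3.1 is itself limited to subjects who stopped without PD. That limit is largely redundant if PD subjects never attend, so the section does not fit together well internally either.

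**2. Length of the gap.**

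Inputs: dosing on Days 1-5 of a 28-day cycle (3.1), so the last dose is on Day 5 and the next cycle is planned for Day 29. Scans fall within the 7 days before the planned next cycle (5.2.2.17). Cycles may be delayed by up to 7 days (4.5.2). Assumption: the End of Treatment visit takes place on the day of the scan; a later visit shortens the gap.

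Formula: gap = 30 − (End of Treatment day − last dose day), with a minimum of 0.

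- No delay, scan on Day 22: 22 − 5 = 17 days after last dose; gap = 30 − 17 = 13 days (13/30 = 43%).
- No delay, scan on Day 28: 28 − 5 = 23 days; gap = 30 − 23 = 7 days (7/30 = 23%).
- 7-day delay (next cycle Day 36), scan on Day 29: 29 − 5 = 24 days; gap = 6 days.
- 7-day delay, scan on Day 35: 35 − 5 = 30 days; gap = 0.
- PD found off schedule, assuming End of Treatment 0-10 days after last dose: gap = 30 to 20 days. The protocol gives no frequency for this case.

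**3. Effect on the endpoint.**

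The share of treated subjects with an unrecorded late event would be s × q × (1 − c), where s is the share stopping for PD, q the chance of a new AE in the gap and c the chance it is captured without a visit. The protocol gives none of the three. Purely as assumptions, s = 50%-90%, q = 10%-30% and c = 0%-50% give 0.5 × 0.1 × 0.5 = 2.5% at one end and 0.9 × 0.3 × 1 = 27% at the other. A range that wide is not an estimate; it shows that the size cannot be taken from the document.

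**The case against.** The strongest reply is that the waiver removes a visit and not a duty. Section 6.4.1 keeps AE reporting open to 30 days for everyone, 4.2.3 still calls for safety follow-up, and 5.2 tells subjects to call about abnormalities between visits and has sites obtain records of unscheduled care elsewhere. Days 8, 15 and 22 and the End of Treatment visit already cover much of the window, and End of Treatment includes laboratory and antibody samples. The study is single-arm, its AE summaries are descriptive, and no comparison by reason for stopping is planned.

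Most of this stands, and it limits the point. A reader might infer that PD subjects go unobserved for the whole 30 days, or that the primary percentages are shown to be too low in the largest group of subjects. The documents support neither: earlier assessments fall inside the window, the protocol does not give the share stopping for PD, and under-reporting is possible but not demonstrated.

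A reader might also infer from 6.4.2.1 that SAEs are lost while non-serious AEs from the same days are collected. That does not follow. Under 6.1.2 an SAE is a kind of AE, 6.3.1 has AEs recorded on the CRF with an assessment of seriousness, and the 6.4.1 window has no cutoff at new therapy. Section 6.4.2.1 also keeps suspected related SAEs reportable after study completion. What remains is a mismatch of wording between two reporting periods.

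The reply does not remove the contradiction between 5.2.3.1 and sections 4.2.3 and 5.3.1, or the absence of a scheduled assessment at the end of the window for one group of subjects only.

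**Conclusion.** The point holds as a contradiction that bears on a primary safety endpoint and should be corrected. The supportable size is about 7-13 of 30 days without a scheduled AE/SAE assessment when PD is found at a scheduled scan with no cycle delay, taking End of Treatment to be on the scan day. The consequence is possible under-ascertainment late in the window that differs by reason for stopping. DLT and MTD evaluation is not directly affected, because it rests on the first 28-day cycle (4.5.4.2, 7.2).

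**What to change.** - **5.2.3.1:** require an AE/SAE and concomitant-medication contact at 30 (±3) days after last dose for all treated subjects, with telephone acceptable after PD. The existing limit on the scan can stay.
- **4.2.3, 5.3.1 and Table 5.2-2:** state which day-30 specimens, weight, vital signs and ECG are or are not required after PD, so that these sections agree with 5.2.3.1. A telephone contact does not supply these items, so this has to be settled separately.
- **6.4.2.1:** align the SAE period with 6.4.1 and 7.3.1, and flag events that start after new anticancer therapy in the analysis.

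The contact costs one telephone call per subject who stops for PD and brings the gap to zero, subject to the ±3-day window. No sample size or error rate changes. Any cost of day-30 samples and measurements depends on what the sponsor decides to require after PD.

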5.3.7 Disease Evaluation and Methods

Survival will be followed approximately every 3 months beginning at 3 months post-treatment by clinic visit or telephone (beginning at 6 months post-treatment) until the end of the study.

Tumor measurements and assessments will be based on RECIST v 1.1 ([Eisenhauer et al, 2009](#)) and will be performed at time points as specified in [Table 5.2-1](#) and [Table 5.2-2](#). Additional tumor measurements may be performed at the discretion of the investigator or according to institutional practice. In subjects who achieve a complete or partial response to treatment, tumor measurements will be repeated for confirmation at least 4 weeks later using the same imaging tests. The same tumor assessment method should be used throughout the study.

Tumor measurements must be recorded in metric notation by use of a ruler or calipers, and the same method/technique of tumor assessment must be used throughout the study.

Imaging-based evaluation is preferred to evaluation by clinical examination when both methods have been used to assess the antitumor effect of the treatment. The analysis for tumor response will be based on the investigator's assessment during the conduct of the study.

Tumor assessments may include the following evaluations: physical examination, CXR, CT, or MRI scan of the chest, abdomen, and pelvis, and CT or MRI scan of the brain. CT or MRI scan of the brain will be performed if the subject is neurologically symptomatic. The same method must be used for all subsequent tumor assessments.

- **Physical examination.** Lesions detected by physical examination will only be considered measurable if superficial, eg, skin nodules and palpable lymph nodes. Documentation by color photography including ruler is recommended for estimating the size of skin lesions.
- **Chest x-ray.** Lesions considered acceptable for measurement on chest radiograph should be clearly defined and surrounded by aerated lung. However, CT is preferable.
- **CT scans of the chest, abdomen, and pelvis.** CT scans should be performed with contiguous cuts in slice thickness of 10 mm or less. Spiral CT should be performed using a 5-mm contiguous reconstruction algorithm.

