Progression-free survival will be measured from the start of treatment with MEDI-565 until the documentation of disease progression or death due to any cause, whichever occurs first. Disease progression is defined according to RECIST guidelines. Progression-free survival will be censored on the date of last tumor assessment documenting absence of tumor progression for subjects who have no documented progression and are still alive prior to data cutoff, dropout, or the initiation of alternate anticancer treatment. Subjects having no tumor assessments after the start of treatment with MEDI-565 will have PFS censored on the first date of treatment with MEDI-565. PFS will be evaluated using the Kaplan-Meier method ([Kaplan and Meier, 1958](#)).

Overall Survival

Overall survival will be determined as the time from the start of treatment with MEDI-565 until death. For subjects who are alive at the end of study or lost to follow-up, OS will be censored on the last date when subjects are known to be alive. The OS will be evaluated using the Kaplan-Meier method ([Kaplan and Meier, 1958](#)).

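### Protocol 5.2.3.3 ends the 3-monthly contacts at disease progression, contradicting the rules in 4.2.3 and 5.3.7 that survival is followed to death or end of study; if sites follow 5.2.3.3, overall survival is biased upward

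*Protocol*

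**What the plan says.** Section 5.2.3.3 covers the contact at 6 months after treatment and every 3 months thereafter. It has three items: subsequent anticancer therapy, survival status ("Record survival status") and a conditional scan. Its stopping rule applies to the contact as a whole: "Visits every 3 months post-treatment should be continued until disease progression is documented". The same section adds "This visit may be conducted by telephone if CXR, CT, or MRI scan is not completed", and limits the scan as "only for subjects who discontinued treatment without progressive disease and who have not initiated an alternative anticancer therapy".

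Other sections set a different end for survival follow-up:

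- Section 4.2.3, on subjects permanently off investigational product, has two tracks. Disease evaluations stop at progression, among other events. Survival is followed "for survival every 3 months until death, withdrawal of consent, or end of study".
- Section 5.3.7: "Survival will be followed approximately every 3 months beginning at 3 months post-treatment", by clinic visit or telephone, to the end of the study.
- Section 3.2 follows all subjects to the end of the study.
- Table 5.2-2 lists survival status and subsequent anticancer therapy in its 3-monthly column, with no stop at progression.
- Section 7.3.2.3, for subjects alive at the end of study or lost to follow-up: "OS will be censored on the last date when subjects are known to be alive". Progression is not a censoring event for OS.

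**The concern.** The stopping rule that section 4.2.3 gives to disease evaluation appears in 5.2.3.3 attached to the contact that also collects survival data. Under section 3.2, treatment runs to confirmed progression unless something else ends it first, and the population has no standard or curative option. Progression is therefore likely to be a common reason for stopping, although the protocol gives no rate. For a subject who stops for progression, it is already documented before the first 5.2.3.3 contact falls due, so read literally none of those contacts takes place.

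OS would then be censored at the last contact for a reason that predicts death. Kaplan-Meier estimation assumes that censored subjects have the same later risk as those still followed. Here the subjects still followed would be mainly those without progression, so the later part of the curve would sit too high. Records of subsequent anticancer therapy would be lost for the same subjects.

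**Working it through.** **1. When survival contact ends, section by section**

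| Protocol section | Survival contact ends at |
|---|---|
| 5.2.3.3 (6 months onward) | documented progression |
| 5.2.3.2 (3-month visit) | single visit, survival recorded, no progression stop |
| 4.2.3 | death, withdrawal of consent, or end of study |
| 5.3.7 | end of study |
| 3.2 | end of study |
| Table 5.2-2, 3-monthly column | no stop given |

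Section 5.2.3.3 cannot be carried out together with 4.2.3 and 5.3.7 for a subject with progression.

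**2. What 5.2.3.3 alone leaves for a subject who stops treatment for progression**

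- End of Treatment visit: held.
- 30-day visit (5.2.3.1): required only for subjects who stop for another reason.
- 3-month visit (5.2.3.2): held, survival status recorded.
- 6 months onward: none.

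The last scheduled survival contact is the 3-month visit, not the date of progression.

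**3. Illustration of the size**

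The protocol gives no progression or survival times, so every input here is an assumption:

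- time to progression (TTP) exponential, median 2 or 3 months (mean = median / ln 2), with treatment stopped at progression;
- post-progression survival (PPS) exponential, median 3, 5 or 8 months;
- death without progression exponential, mean 20 months;
- study end uniform between 12 and 24 months;
- 200,000 simulated subjects per scenario, so the differences are essentially bias rather than chance.

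For a subject who progresses, OS = TTP + PPS; otherwise OS is the time to death without progression. Follow-up is compared under two rules:

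- Full (4.2.3 and 5.3.7): observed time = min(OS, study end).
- 5.2.3.3 followed literally, with the 3-month visit held: observed time = min(OS, TTP + 3, study end) for subjects who progress.

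| Median TTP / PPS (months) | Median OS, full | Median OS, contact ends at 3-month visit | 12-month OS, full | 12-month OS, contact ends at 3-month visit |
|---|---|---|---|---|
| 2 / 3 | 5.08 | 5.30 | 12% | 18% |
| 2 / 5 | 6.79 | 7.31 | 25% | 31% |
| 2 / 8 | 9.22 | 9.87 | 40% | 43% |
| 3 / 3 | 5.82 | 6.21 | 17% | 24% |
| 3 / 5 | 7.50 | 8.26 | 29% | 35% |
| 3 / 8 | 9.77 | 10.64 | 42% | 46% |

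The median rises by 0.22 (5.30 − 5.08) to 0.87 (10.64 − 9.77) months. The 12-month figure rises by 3 (43 − 40) to 7 (24 − 17) points. All six scenarios move upward.

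**4. The extreme case, for contrast**

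If contact ended at progression itself, the simulation gives a median of about 14 months and 12-month OS of about 55% in every scenario. Both follow directly from the assumed hazard of death without progression: median = 20 × ln 2 = 13.9 months, and exp(−12/20) = 0.55. No post-progression death would enter the curve at all. For subjects who stop treatment for progression, the 3-month visit rules this case out.

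**The case against.** The strongest reply is that the protocol, read as a whole, already follows survival past progression. Section 4.2.3 separates the two tracks, 5.3.7 and 3.2 run to end of study, Table 5.2-2 has no progression stop, and 7.3.2.3 does not censor OS at progression. Under section 4.6 a subject completes the study only by being followed to its end. Section 4.2.3 requires documented attempts to re-establish contact with missing subjects. Even within 5.2.3.3, allowing a telephone contact without a scan, and withholding the scan from subjects who stopped with progression, makes most sense if those subjects are still contacted. On this view the sentence was meant for disease assessment only.

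That is probably the intent, and it defeats a stronger reading that a reader might infer: that the protocol prescribes informative censoring of OS, so that every death after progression and after the 3-month contact is lost and the median rests on a selected minority. The documents do not support that. Such losses occur only where a site follows 5.2.3.3 over 4.2.3 and 5.3.7, and nothing shows which section sites would follow.

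The contradiction still stands. Section 5.2.3.3 is the detailed instruction for this visit, its stopping sentence is not limited to the scan, and no text says which section governs.

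**Conclusion.** This is an internal contradiction over when survival contact ends, not a decision to stop survival follow-up at progression. Any bias is conditional on sites acting on 5.2.3.3, and its direction is then upward. Its size depends on assumed times: about 3 to 7 points at 12 months and 0.2 to 0.9 months in the median if every site did so and all held the 3-month visit. Mixed practice across sites would be expected to give less. The shift to a median of about 14 months should not be cited as the likely effect.

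For scale, in one 20-subject expansion arm with 12-month OS of 29%, the standard error ignoring censoring is √(0.29 × 0.71 / 20) = 0.10, or 10 points. The illustrated bias is smaller than that, but it is systematic and avoidable.

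OS is one of six descriptive secondary efficacy measures. The primary endpoints concern dose-limiting toxicity, dose selection and safety, and the only power statement (section 7.5) concerns response rate. No sample size, error rate or escalation rule is affected. Severity is moderate to minor.

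**What to change.** Reconcile 5.2.3.3 with 4.2.3 and 5.3.7 by replacing its stopping sentence with text to this effect: disease assessments by imaging continue every 3 months until progression or the start of another anticancer therapy, subject to the other stops in 4.2.3; survival status and subsequent anticancer therapy are recorded every 3 months for all subjects, by telephone if needed, regardless of progression, until death, withdrawal of consent or end of study. A matching footnote to the 3-monthly column of Table 5.2-2 would keep the schedule and the text aligned.

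The cost is a sentence or two and a footnote. Sections 4.2.3 and 5.3.7 already require the survival contacts, 5.2.3.3 already allows the telephone, and subsequent therapy can be recorded in the same call. No added visits or imaging are needed, and no analysis rule changes.
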